Hypothesis: 15-F2t-isoprostane will be significantly increased in RYR1-RM myopathy patients compared to healthy individuals.

Hypothesis: 6MWT distance will be significantly decreased in RYR1-RM patients compared to healthy individuals.

- 2) After 30 participants complete their 2nd visit at 6 months (prior to starting study drug/placebo), disease progression will be assessed using paired t-tests to determine changes between 0 and 6 month visits for each outcome measure. For the primary outcome measures, 15-F2t-isoprostane and 6MWT will be assessed for change between 0 and 6 months. This analysis will be repeated when all 6 month visits are completed.

Hypothesis: 15-F2t-isoprostane concentration will not change significantly between 0 and 6 months in RYR1-RM myopathy patients.

Hypothesis: 6MWT distance will not change significantly between 0 and 6 months in RYR1-RM patients.

The purpose of the above interim look analyses (under #1) is to confirm that the affected subjects are different from healthy individuals. Because of the rolling nature of the study and the length of time involved to complete the first phase of the study, this allows evaluate whether these outcomes are different from healthy individuals, as expected, in order to confidently proceed with the study. The purpose of the above interim look analysis (under #2) is to characterize the natural history and variability of the RYR1-RM patients for these specific outcome measures and to contribute novel data to the field of RYR1 as soon as possible for future trial design, given that an N of 30 is a large number in rare disease.

Optimal measures for fatigability in RYR1-RM will be determined using paired t-tests for 6MWT distance and speed, time for graded functional tests, and fatigue index for biodex fatigue test. Correlative analysis (Pearson correlation and/or Spearman rho) will be used to examine the linear relationship between subjective fatigue measures (FACIT and MFI) and the salivary fatigue biomarker to the objective fatigability measures mentioned above as well as to compare forced vital capacity to slow vital capacity. Spearman rho correlation, Pearson correlation and or Bland Altman analysis will also be used to examine the relationship between slow vital capacity and forced vital capacity.

Reliability will be assessed for PROMIS, FACIT, MFI, MFM, and NeuroQoL by Cronbach's alpha for internal consistency and by Intraclass correlation coefficient for test-retest. If the test-

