There will be no difference in mean corrected 15-F2t-isoprostane concentration or 6MWT distance, between the *RYR1*-RM and otherwise healthy individuals.

Alternative Hypothesis (H_1)

Corrected 15-F2t-isoprostane concentration will be significantly increased and 6MWT total distance will be significantly decreased in *RYR1*-RM myopathy patients when compared to otherwise healthy individuals.

2. After 30 participants complete their 2nd visit at 6 months (prior to starting study drug/placebo), disease progression will be assessed using paired t-tests to determine changes between 0 and 6-month visits for each outcome measure. For the primary outcome measures (corrected 15-F2t-isoprostane concentration and 6MWT) change between 0 and 6-month time points will be assessed. This analysis will be repeated when all 6-month visits are completed.

Null Hypothesis (H₀)

Corrected 15-F2t-isoprostane concentration and 6MWT total distance will not change significantly between 0 and 6 months in *RYR1*-RM myopathy patients.

Alternative Hypothesis (H₁)

There will be a statistically significant difference between 0 and 6-month values for corrected 15-F2t-isoprostane concentration and/or 6MWT total distance in *RYR1*-RM myopathy patients.

Intervention phase analyses (month 6 to month 12)

- Use an independent t-test (or non-parametric equivalent) to compare pre-intervention (month 6) values for demographics, urine isoprostane and six-minute walk test between NAC versus placebo groups.
- Using multiple imputation (x40 datasets and minimum/maximum value constraints from *per protocol* data) impute missing month 12 data.
- The following GLM should be run both *per protocol* and with ITT datasets.
 1. Run a general linear model comparing month 12 month corrected 15-F2t-isoprostane concentration (corrected_f2-isop_month12, corrected_f2-isop_PGF2alpha_ratio_month12) between NAC and placebo groups controlling for pre-intervention value. Run this model again controlling for established *a priori* confounders including age, sex, height, weight, BMI, smoking status, alcohol status. Variables that do not contribute significantly to the model may be removed. (Exclude RYR023, RYR024, and all healthy volunteers).

Null Hypothesis (H₀)

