There will be a statistically significant difference between 0 and 6-month plasma GSH:GSSG, and/or CYS:CYSS ratios and/or corrected DCF-fluorescence intensity in *RYR1*-RM myopathy patients.

Aim 2: Timed function tests; Biodex; Myotools, MFM, MRI, PROMIS, FACIT, MFI, NeuroQoL scales.

1. We will compare baseline outcome measure values against healthy controls, when possible, using a summary independent t-test (or non-parametric

equivalent). When sufficient normative data is available, Hedge's g may be used to calculate the standardized mean difference between groups.

Null Hypothesis (H_0)

There will be no difference, in graded functional tests (time to completion); Biodex (fatigue indices); Myotools values (grip and pinch strength), MFM (D1, D2, D3 and total % of maximum score), MRI (intramuscular fatty infiltration), PROMIS (scale scores), FACIT (total score), MFI-20 (total score), NeuroQoL (scale scores), between *RYR1*-RM and otherwise healthy individuals.

Alternative Hypothesis (H_1)

In *RYR1*-RM patients, graded functional tests (time to completion); Biodex (fatigue indices); Myotools values (grip and pinch strength), MFM (D1, D2, D3 and total % of maximum score), PROMIS (scale scores), FACIT (total score), NeuroQoL (scale scores) will be significantly lower and MRI (intramuscular fatty infiltration), MFI-20 (total score) significantly higher when compared to otherwise healthy individuals.

2. We will compare baseline outcome measure values against values obtained at 6 months using paired t-tests (or non-parametric equivalent) to determine changes between 0 and 6-month visits for each outcome measure.

Null Hypothesis (H_0)

Graded functional tests (time to completion); Biodex (fatigue indices); Myotools values (grip and pinch strength), MFM (D1, D2, D3 and total % of maximum score), MRI (intramuscular fatty infiltration), PROMIS (scale scores), FACIT (total score), MFI-20 (total score), NeuroQoL (scale scores), will not change significantly or clinically between 0 and 6 months in *RYR1*-RM myopathy patients.

Alternative Hypothesis (H_1)

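### The Phase 1 no-change hypotheses for isoprostane and 6MWT are tested by paired t-tests with no margin or confidence-interval criterion, so a non-significant result cannot support them

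*Protocol*

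**What the plan says.** Protocol section 10.a, Natural history study, approach 2, states that "disease progression will be assessed using paired t-tests to determine changes between 0 and 6 month visits for each outcome measure". The hypotheses for the two primary outcomes are "Hypothesis: 15-F2t-isoprostane concentration will not change significantly between 0 and 6 months in RYR1-RM myopathy patients" and "Hypothesis: 6MWT distance will not change significantly between 0 and 6 months in RYR1-RM patients". The first analysis is an interim look once 30 patients have had their 6-month visit; then "This analysis will be repeated when all 6 month visits are completed". The reason given for the early look is descriptive: "The purpose of the above interim look analysis (under #2) is to characterize the natural history and variability of the RYR1-RM patients". It is also meant to supply data for the design of later trials.

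The SAP (Natural history phase analyses, item 2) keeps the method: "disease progression will be assessed using paired t-tests to determine changes between 0 and 6-month visits for each outcome measure". It places no significant change under H0 and a significant difference under H1.

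For the Aim 2 secondary measures (SAP, Secondary Outcome Measures, Natural History Phase, item 2), H0 is that nine measures "will not change significantly or clinically between 0 and 6 months in" patients. The matching H1 is a difference that is statistically significant and/or clinically meaningful. No threshold for clinical change is named for any of the nine.

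Neither document gives a margin, a confidence-interval criterion or a power statement for the 0-6 month comparison.

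**The concern.** The protocol predicts no change and tests it with a procedure whose null is also no change. Every p > 0.05 then agrees with the prediction, and agreement is more likely the smaller the sample or the noisier the measure. A paired t-test can show that a change occurred. Without a margin or an interval it cannot show that no change of importance occurred.

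The Introduction (section 1) says natural-history data on oxidative stress, fatigability and fatigue are lacking, and that the first part of the study is there to fill that gap. If a non-significant result is reported as no change, later trials in this rare disease may assume a flat untreated course that the data do not establish.

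The step from non-significance to a positive property has already been taken once. In section 10.b, in the case for making isoprostane the primary oxidative stress measure, the absence of a significant difference between baseline and untreated 6-month values is offered as a sign that the biomarker is reliable in these patients. That is a claim about reliability, for isoprostane only, but the reasoning is of the same kind.

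**Working it through.** **The plan's own figure.** No sample-size or power figure is given for the Phase 1 paired comparison. The only calculation with stated inputs is for Phase 2 glutathione (section 10.b: delta 1.7, SDs 2.34 and 2.80, two-sided 0.05, 80% power, 38 per group). It reproduces (Satterthwaite t-test: power 79.8% at 37 per group, 80.9% at 38) but has no bearing on this point.

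**Inputs**
- Interim n = 30 (Protocol section 10.a, approach 2).
- Final n = 76: an assumption. It is the completer target in section 3.a. The number of 6-month visits is not stated, and section 10.b says the study is being closed to data analysis.
- Alpha = 0.05, two-sided: an assumption for Phase 1. The protocol states 0.05 for Phase 2 and for the healthy-volunteer comparison, not for these paired tests.
- True change d, in units of the SD of the 0-6 month change. The documents give no such SD, so a range is shown.

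**Chance of a non-significant result.** The paired t statistic has n − 1 degrees of freedom and noncentrality d√n. The chance is the probability that it falls between −t and +t, where t is the 97.5% point: 2.045 at n = 30 and 1.992 at n = 76. For d = 0.3 the noncentrality is 0.3 × √30 = 1.643 and 0.3 × √76 = 2.615.

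| True change (SD of change) | n = 30 | n = 76 (assumed) |
|---|---|---|
| 0.2 | 81% | 59% |
| 0.3 | 64% | 27% |
| 0.4 | 44% | 7% |
| 0.5 | 25% | 1% |

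A true change of 0.53 SD is needed for 80% power at n = 30, and 0.33 SD at n = 76.

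**What an interval would show.** The 95% CI half-width is t/√n: 2.045/√30 = 0.37 SD and 1.992/√76 = 0.23 SD. Take an observed mean change of 0.2 SD:
- n = 30: t = 0.2 × √30 = 1.10, below 2.045, so non-significant. The 95% CI is 0.20 ± 0.37, or −0.17 to 0.57 SD.
- n = 76: t = 0.2 × √76 = 1.74, below 1.992, so non-significant. The 95% CI is 0.20 ± 0.23, or −0.03 to 0.43 SD.

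Both would count as no significant change, yet the first leaves a change of more than half an SD open.

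**What an equivalence rule could deliver.** Require the 90% CI to lie inside ± the margin, and suppose the true change is zero. The smallest margin with 80% power is then 0.55 SD at n = 30 and 0.34 SD at n = 76. At n = 30 a tighter margin would often give an inconclusive result: at 0.3 SD the rule succeeds 5% of the time, against 66% at n = 76. These margins describe precision only and are not proposals.

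**The case against.** A reader might infer that the plan decides the question at n = 30 and concludes stable disease from non-significance. The documents do not support that. The look at 30 is interim and the same test is repeated at completion. Its stated purpose is to describe natural history and variability. No sentence makes p > 0.05 proof of stability. The SAP sets out an ordinary difference test, in which failing to reject H0 confirms nothing. All of this stands.

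It also stands that nothing in the trial's conduct turns on approach 2. It carries no go/no-go rule; the wording about proceeding with confidence belongs to the comparison with healthy individuals in approach 1. The Phase 2 analysis compares NAC with concurrent placebo and adjusts for the starting value, so it does not assume a stable untreated course. The Introduction also names the MFM as its main gauge of progression, so the natural-history picture does not rest on the two primary outcomes alone.

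The Aim 2 secondary measures are a different case. Because H1 there includes a clinically meaningful difference, non-significance alone would not mean stability. The fault is only that clinical change is undefined.

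The objection does not remove the mismatch in the protocol. Its research hypothesis is still one of no significant change, the only stated test cannot support it, nothing tells the analyst how to word a non-significant result, and section 10.b shows such a result being read as positive evidence.

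**Conclusion.** The point holds in a limited form. A non-significant paired t-test cannot support the stated no-change hypotheses for isoprostane and 6MWT. At n = 30 it is the more likely outcome even when the true change is 0.3 SD (64%), and changes of 0.2 to 0.3 SD are still often missed at 76 (59% and 27%). These figures assume a two-sided 0.05 level, effects in SDs of the paired change, and a final n equal to the completer target. If the final number lies between 30 and 76, the miss rates lie between the two columns.

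The consequence is confined to what Phase 1 may claim about natural history. The randomised comparison is not affected, and the documents do not show a stability conclusion already drawn for either primary outcome. The change is worth making because natural history is a declared product of the study and the correction needs no new data.

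**What to change.** 1. In Protocol section 10.a (approach 2) and SAP Natural history phase analyses (item 2), make the mean 0-6 month change with its 95% CI the main natural-history result for each measure, at the interim look and at completion.
2. State that p > 0.05 will be reported as a change of up to X not excluded, with X taken from the CI limit, and never as no change.
3. Allow a claim of stability only where the 90% CI lies within a margin that is clinically anchored and justified from outside these data. Disclose when each margin was chosen: section 10.b shows that the isoprostane comparison has been seen, and the SAP (July 2, 2018) names data files locked with a March 29, 2018 date. Do not use ±0.5 SD of change as a default. In metres or concentration units it widens as the measure gets noisier, which repeats the fault, and for isoprostane it would be set after the data were seen.
4. In the SAP Aim 2 secondary hypotheses, tie clinical change to a named threshold for each measure or delete the term from both H0 and H1.

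The cost is a few sentences and one or two intervals per measure from data already collected. The drawback is that some measures, especially at n = 30, will be reported as inconclusive. Where no external margin exists, the 95% CI alone is sufficient.

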The primary analysis will be an intent-to-treat (ITT) analysis, i.e. all randomized participants will be included in the analysis. The mechanism for missing data will be evaluated. If missing data are unrelated to the intervention or primary outcome (i.e. missing completely at random or missing at random), the analysis will be based on multiple imputations (20-40 imputed datasets, depending on the extent of the missing data) with a pooled average of the 20-40 imputations included in the final dataset and used in hypothesis-testing analyses. Minimum and maximum value constraints for imputed data will be determined using *per protocol* averages.

Because of uncertainties regarding the true effect size of NAC treatment in our patient population, and the rare nature of this disease possibly limiting accrual, we plan to perform a sample size reevaluation and interim analysis once 30 patients have completed the trial, i.e., when 40% of our potentially achievable accrual reach Month 12.

For the sample size reevaluation, and based on the observed data so far, we will calculate the following: the control group delta and its standard deviation and the standard deviation of the delta for the active arm. Based on these observed parameter values for urine 15-F2t-isoprostane, we will re-calculate the sample size and compare it to the current N=76.

Based on O'Brien-Fleming boundary calculations (O'Brien and Fleming, 1979), the interim analysis will result in one of 3 actions:

1. If there is strong indication of no benefit of NAC in decreasing 15 F2t-isoprostane levels, i.e. if the observed standardized treatment effect is less than -3.36, we will consider stopping the study early for futility.
2. If there is no clear indication of benefit of NAC decreasing 15 F2t-isoprostane levels, i.e. if the observed standardized effect size is between -3.36 and 3.36, we will continue the study and analyze the data at the completion of the study.
3. If there is strong indication that the NAC treatment decreases 15 F2t-isoprostane levels, i.e. if the observed standardized treatment effect is greater than 3.36, we will consider stopping the study early for efficacy.

Stopping the trial early when there is strong evidence for futility or efficacy will reduce patient burden, decrease excess costs, and provide a potential treatment sooner for this rare disease, which currently has no treatment.

The primary outcome measure is being changed, initially due to pipette calibration error in the lab at NIH. Additional review of our data at Emory after sending a second batch of samples and

further literature review identified further justification for changing the primary oxidative stress biomarker from glutathione (GSH) to 15-Ft2-isoprostane:

- The processing of GSH and its oxidized form GSSG often results in methodological artifacts. For instance, sample acidification for protein precipitation leads to an increase in GSSG levels thus decreasing GSH:GSSG ratio (Marrocco et al. 2017). The assay is sensitive to exposure to air/time and sample volume and is therefore prone to error. The aforementioned methodological artifacts are not unique to this protocol and have been described previously (McGill et al. 2015).
- During the current protocol, such methodological issues arose at Emory in addition to the pipette calibration issue at NIH. For example, when the second sample for each patient was rerun at Emory, including samples unaffected by the pipette error, the results between the first patient and second patient sample were unreliable. These methodological errors in GSH as a biomarker and the recurrent, significant time delays for processing by Emory, in addition to the pipette error, prompted a change in primary outcome measure from GSH to 15-Ft2-isoprostane.
- 15-Ft2-isoprostane was collected on each individual at each visit as a secondary outcome measure for oxidative stress throughout the life of the protocol. The change from GSH to 15-Ft2-isoprostane is being made prior to treatment allocation un-blinding and prior to statistical analyses, which is the optimal time to change a primary endpoint when such a change is required (Evans, 2007). Changes in primary endpoints are reported in approximately 30% of clinical trials (Ramagopalan, 2014).
- Elevated oxidative stress is a hallmark pathological feature in RYR1-RM and has been identified in several pre-clinical models of the disease (Durham et al. 2008, Dowling et al. 2012, Lee et al. 2017, Michelucci et al., 2017). In particular, lipid peroxidation of mitochondrial membranes has been implicated as a central pathomechanism that leads to severe mitochondrial dysfunction and/or death in the RYR1Y522S/W mouse model (Durham et al. 2008). Notably, treatment of the aforementioned mice with N-acetylcysteine (NAC), (ad lib via drinking water for 8 weeks) rescued lipid peroxidation and concomitantly prevented previously observed decrements in force generation (Durham et al., 2008). These findings have recently been supported by a longer-term study of NAC treatment in the same mouse model in which NAC treatment led to a decreased number of structural cores and improved skeletal muscle function (Michelucci et al., 2017).
- 15-F2t-isoprostane has been reported as the most reliable in vivo biomarker of oxidative stress and is a measure of lipid peroxidation (Milne et al. 2007, van 't Erve et al., 2017). Moreover, a typical 15-F2t-isoprostane concentration has been established through substantial data collection from otherwise healthy volunteers (n= 1881) allowing comparisons to be made to disease populations (van 't Erve et al., 2017). Finally, when our participants' baseline and 6 month (untreated) isoprostane levels were compared, the findings were not significantly different, suggesting reliability of this biomarker in our population, in contrast to our GSH data analysis of the same time points.

--In a recent crossover trial, conducted in 36 individuals with low resting GSH concentrations, NAC supplementation (2 × 600 mg, twice daily, for 30 days) led to a 22% reduction in 15-F2t-isoprostane concentration and improved exercise performance (Paschalis et al. 2017). These findings are pertinent for this protocol as it has been demonstrated pre-clinically that RYR1-RM models have low resting GSH concentrations, and both 15-F2t-isoprostane concentration and improved exercise performance are being tested in our trial. Additional antioxidant clinical trials have also shown a beneficial effect of treatment on 15-F2t-isoprostane concentration. In particular, an α -tocopherol (vitamin E) antioxidant trial in smokers (n= 81 placebo; n= 82 vitamin E) demonstrated that consuming 400 IU vitamin E daily resulted in a statistically significant (21%) difference in corrected urinary F2-isoprostane concentration compared to placebo following 32-months treatment (Guertin et al. 2016).

In combination, these findings strengthen the rationale for using 15-F2t-isoprostane concentration as the primary outcome measure for this protocol in place of GSH. The sample size recalculation for 15-NR-0072 was therefore performed using 15-F2t-isoprostane data from our study. [name], Clinical Center Statistician, was unblinded for the sample size recalculation. All investigators remain blinded until the study is complete. [name] used the current study data on isoprostane levels from participants in the treatment vs. placebo groups to calculate the N required to complete the study. The N achieved was 182, which is not feasible in this rare disease population and the study is being closed to data analysis.

11. Human Subjects Protection

a. Subject selection

Subject selection will be equitable as much as possible due to the rarity of RYR1-related myopathy. All ages within the specified range, races, and both genders will be accepted. Individuals with a genetic mutation in *RYR1* will be prioritized to decrease the rate of screening failures. Individuals with a muscle biopsy showing central cores will be prioritized to decrease the variability in the sample.

Subject selection for healthy volunteers will be equitable.

b. Justification for inclusion of children

Children age 7 years old and older are affected with this disease and are affected with fatigue. This drug in this route of administration has a good safety profile in children at this dose for other indications. Children <7 years of age will be excluded as they will not be able to follow the commands in order to perform all of the outcome measures.

Healthy volunteer children are needed to provide age-matched groups as controls for biomarkers, NIRS, muscle ultrasound, and MRI.

c. Justification for exclusion of other vulnerable subjects

Those unable to provide consent due to cognitive issues will be excluded, due to the requirement to be able to respond to questionnaires such as PROMIS and FACIT.

d. Justification of sensitive procedures (use of placebo)

The use of a placebo is necessary to determine the effects of NAC on this population. Without the placebo, we would not be able to determine if NAC has a significant effect on participants with RYR1-RM. Use of a placebo will allow us to draw stronger conclusions about the effects of NAC than if we conducted the study without a placebo.

e. Safeguards for vulnerable populations (e.g. DPA, pregnancy testing, contraception use, ethics consult, HSPU involvement)

Safeguards: Protections for employees and staff participating in this study include 1) assuring that the participation or refusal to participate will have no effect, either beneficial or adverse, on the subject's employment or position at the NIH, 2) giving employees and staff who are interested in participating the "NIH Information Sheet on Employee Research Participation (Appendix L)" prior to obtaining consent, 3) assuring that there will be no direct solicitation of employees or staff, and, 4) Independent consent monitoring will be provided by the NIH HSPU.

This study collects sensitive information on pregnancy status, which will be in the participant's NIH medical record. The PI will train study staff regarding obtaining and handling potentially sensitive and private information about co-workers through staff discussions and written branch/section procedures. All research activities will be conducted in as private a setting as possible, limiting personnel present.

For pediatric patients, we will have parental consent and minor assent. Pediatric staff and pediatric equipment will be used. During blood draws, a local anesthetic cream such as Eutectic Mixture of Local Anesthetics (EMLA) may be used to minimize the pain for young children. For pediatric participants, no more than 5 mL/kg will be drawn in a single day, and no more than 9.5 mL/kg will be drawn over any eight-week period.

Blood will not be drawn on participants if they are known to be anemic (Hgb < 8 gm/dl) per medical history, or if their medical condition causes an investigator to believe that blood drawing might be detrimental to the participant.

Parents can accompany their child to the MRI suite and watch their child through a window during the procedure. During the procedures, there will be music and/or video to distract the child. All participants will be able to communicate with the MRI staff at all times.

For women of childbearing age, we will do pregnancy testing to exclude women who are pregnant at the beginning of the study. We will also exclude women who are breastfeeding. Women who are sexually active will require contraception. Acceptable contraception includes barrier methods (contraceptive sponge, diaphragm, female and male condoms), hormonal methods (oral contraceptives, the patch, shot/injection, and vaginal ring), implantable devices (implantable rods and intrauterine devices), and permanent birth control methods (sterilization implant and surgical sterilization).

f. Qualifications of investigators

The Principal Investigator has verified that all individuals working on this protocol required to take HRPP training under OHSRP SOP 25 (Training requirements for the NIH Human Research Protections Program) have completed all required training.

[name], ANP-BC is a board certified adult nurse practitioner and the Clinical Director of NINR. When the study was changed to Data Analysis only, she began to provide oversight for the study, but there is no clinical or medical management required for subjects in this phase.

[name]., PNP-BC is an assistant clinical investigator in the Tissue Injury Branch/NINR. She is a board certified pediatric nurse practitioner involved in study design, data analysis, interpretation of results and all procedures. She is an investigator authorized to obtain informed consent from participants.

